## PROTOCOL TITLE: SAFE AND HEALTHY SCHOOLS

If a participant is unwilling or unable to complete an at-home BinaxNOW test, then their study participation is complete after providing the lollipop swab for PCR testing.

For the at-home BinaxNOW testing, the participant will schedule a follow-up virtual visit with the study coordinator. If they are unable to complete a virtual visit, they will schedule an in-person home visit. They will also be sent home with a BinaxNOW testing kit.

The study coordinator will send participants a confirmation email with a unique link to a secure video chat platform, such as Microsoft Teams, Cisco WebEx, or HIPAA-Secure Zoom. They will also send instructions about how to join the meeting link. During the virtual visit, the study coordinator will instruct the family to read the instructions in the BinaxNOW box, do their best to do the test accurately, and ask questions as needed. The study coordinator will also ask if the participant understands and feels comfortable with the instructions, and the study coordinator will offer to demonstrate the steps of the test. The study team member will use the video to observe sample collection and offer tips or suggestions, as needed, to ensure proper collection. They will also ensure that participants take time and care to read the test results accurately, and they will answer any questions that participants may have. The participant or their parent will verbally provide the test results to the study team, and the study team will record the result in REDCap. The completed test card will be observed and the results verified by the study coordinator.

If a participant is unable or unwilling to do a virtual visit for at-home testing, such as they do not have access to technology or do not wish to provide an email address, they will be offered an in-person home visit. The procedures would be the same. If participants are not able to complete the test during the virtual visit, such as inability to collect the sample or accidental tampering with the test card, the study team member will also provide the option of a home visit. At home visits, if participants are unable or unwilling to collect the nasal swab sample themselves, the study coordinator may collect the sample.

After recording the result of the BinaxNOW test, the study coordinator will ask the participant if they think they would have been able to accurately do this test on their own or if help was necessary. The study coordinator will record their response in REDCap. They will also note what type of help was needed, if any. Furthermore, the study coordinator will ask if the adult thinks they would be able to accurately do the test on their own in the future.

The BinaxNOW test kit contains two tests. The second test will be used as a back up, in case the first test is compromised in some way.

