## PROTOCOL TITLE: SAFE AND HEALTHY SCHOOLS

PCR tests are generally performed in hospital or commercial laboratories. They are expensive—usually costing \$75 to \$150 dollars. They also take time to perform; although some tests are run in as short a time as an hour or two; others take 6 to 12 hours. Transportation from the collection site to a centralized testing facility significantly prolongs turnaround time ranging from 1-3 days. These delays limit the use of PCR as a tool for infection control.

The PCR test will be negative during the incubation period because there is not enough virus present to give a positive reaction. Just as the individual is becoming symptomatic, the PCR becomes positive. As the titer of virus peaks during the next 24 to 48 hours, the PCR test stays positive and will remain positive for quite a few more days while the patient is symptomatic and infectious to others. Of importance, the PCR may even remain positive when the patient is no longer infectious to others, because the test detects the nucleic acids even though the virus is no longer capable of replication.

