## 12.0 Study Timelines

12.1 Participation in the study will typically last from 12-72 hours, depending on when the at-home BinaxNOW test virtual visit is completed. When scheduling virtual visits, we will try to schedule as close as possible to 24 hours after the initial in-school test. The target window is no sooner than 12 hours and no later than 72 hours after the in-school test. If it is not completed within 72 hours, the study team will ask the participant to schedule a time to complete the at-home test as soon as possible. If the participant is not able to complete the at-home test within 5 days of enrollment, they will be withdrawn from the study.

We anticipate enrolling all study participants by August, 2022. We intend to complete primary analyses by October, 2022.

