### 20.2 Sample Size Justification:

For Aim 1, it is anticipated that the majority of initial BinaxNOW tests will be negative. It is hypothesized that the proposed two-day serial testing procedure using BinaxNOW tests in participants with an initial negative test will identify true negatives in >95% of participants. The primary diagnostic outcome measure will be the negative predictive value (NPV). The NPV of BinaxNow is ~91% in symptomatic subjects. For the proposed study, the NPV after the second test (24 hours after the first negative results), is assumed to be substantially higher than 91% since the first test was already negative. In order to detect a true NPV after the second test of at least 95% with 90% power at the one-sided 0.05 significance level, a sample size of N=358 participants with an initial negative test is required. To reach a sample size of N=358 participants with an initial negative test, BinaxNOW kits will be administrated to 400 participants. We intend to continue enrolling until we reach the target sample size of N=358 completing the at-home BinaxNOW test.

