## PROTOCOL TITLE: SAFE AND HEALTHY SCHOOLS

This study will be conducted at elementary schools, via virtual visits by staff in a private, quiet location, and at participant homes.

If participants receive a positive at-home BinaxNOW test, we will refer them to their healthcare provider. We will also verify the results of the nasal PCR which will govern the management of return to school.

Study team members will meet and/or communicate regularly to ensure that all persons assisting with the research are adequately informed throughout the study about the currently approved protocol, the research procedures, and their duties and functions. Any changes to the protocol and/or consent/assent will be communicated via email to all study team members conducting study activities.

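### The at-home card is read by eye in a window when the nasal PCR result may already be known, with no masking of the coordinator and no record of what the family knew, so Aim 1 accuracy may be overstated

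*Combined protocol and SAP*

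**What the plan says.** **Who reads the card.** Section 2.3 describes a visual test in which two lines mean positive. Under section 13.3 the participant or parent states the result aloud, the coordinator helps them read carefully and answers questions, the result goes into REDCap, and "The completed test card will be observed and the results verified by the study coordinator". Section 16.1 repeats the verification as quality control.

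**When.** Section 12.1 aims for about 24 hours and sets the limits: "The target window is no sooner than 12 hours and no later than 72 hours after the in-school test". Section 2.3 says that transport of PCR specimens to a central laboratory "significantly prolongs turnaround time ranging from 1-3 days".

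**Where the PCR result goes.** It goes to the school, where it decides return to class (18.1), and to the study team (13.3, 16.5). For Exact Sciences the team sends a result request. ACL matches the nasal swab to the lollipop requisition and returns both results. Section 25.1 adds: "We will also verify the results of the nasal PCR which will govern the management of return to school".

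**What is recorded.** Section 13.4 lists specimen collection times, times of study activities and results. It does not list when the PCR result was released or learned. Cards are discarded after use (19.1), so they cannot be re-read.

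**How it is used.** Section 20.4 reports sensitivity, specificity, PPV and NPV for Aim 1. Section 20.3 requires a nasal PCR result for inclusion. No section masks either reader or sets the order of card read and PCR look-up.

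**The concern.** When the reader of a subjective test may know the reference result, doubtful readings can drift toward it. Here a PCR-positive participant's card that would have been called negative may be called positive, and the reverse for a PCR-negative participant. Both shifts increase agreement with PCR. They raise sensitivity, specificity and NPV together, in the direction of the Aim 1 claim, and a larger sample does not remove them.

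The setting also differs from the intended use. If serial antigen testing replaced PCR, no PCR result would be available when the second card was read. Coordinator verification protects technique and transcription, but it is no protection against this bias if the verifier may know the reference.

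**Working it through.** **1. Timing.** Card read: 12 to 72 h after the in-school test (12.1). PCR turnaround: 1 to 3 days, that is 24 to 72 h (2.3). Overlap: 24 to 72 h. The 24-hour target sits at the start of the overlap.

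**2. The plan's own sample size.** Section 20.2 gives the inputs: "The NPV of BinaxNow is ~91% in symptomatic subjects"; "In order to detect a true NPV after the second test of at least 95"%; "with 90% power at the one-sided 0.05 significance level". It concludes that "a sample size of N=358 participants with an initial negative test is required".

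- Exact one-sample binomial: the smallest N with power of at least 90% is 358. Success needs at least 335 true negatives of 358. P(X ≥ 335 | 358, 0.91) = 0.0487 and P(X ≥ 335 | 358, 0.95) = 0.909. The plan's figure reproduces.
- Normal approximation: [(1.645√(0.91×0.09) + 1.282√(0.95×0.05)) / 0.04]² = 351.6, so 352, which is close.

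Success therefore allows 358 − 335 = 23 false negatives. At NPV 91% the expected number is 358 × 0.09 = 32.2; at 95% it is 358 × 0.05 = 17.9. The gap between an expected null result and success is 32.2 − 23, or about 9 to 10 readings (under 3% of 358).

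**3. Illustration of reading bias.** Assume a true NPV of 91%, and let k be the share of missed PCR-positive cards called positive because the PCR result is known. The documents give no value for k. As in the plan, 358 is used as the NPV denominator.

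- (a) Apparent NPV q = 0.91 / [0.91 + 0.09(1 − k)]; false success = P(X ≥ 335 | 358, q).
- (b) Misses follow Bin(358, 0.09(1 − k)); false success = P(misses ≤ 23).
- (c) As (b), but each shifted card leaves the NPV denominator and the exact 5% cut-off is reset for the smaller number.

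| k | q | (a) | (b) | (c) |
|---|---|---|---|---|
| 0 | 91.0% | 4.9% | 4.9% | 4.9% |
| 5% | 91.4% | 8.2% | 8.6% | 6.3% |
| 10% | 91.8% | 13.1% | 14.2% | 10.2% |
| 20% | 92.7% | 29.6% | 32.9% | 25.6% |
| 30% | 93.5% | 54.0% | 59.3% | 49.8% |

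For k = 10% in (a): q = 0.91/0.991 = 0.9183. With the cut-off held at 335 the answer is 13-14%; resetting it gives about 10%.

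**4. Effect on all three measures.** Assume 10% PCR-positive among initial negatives, second-test sensitivity 50%, specificity 98%, and k = 20% applied to both kinds of error. Sensitivity becomes 0.50 + 0.50 × 0.20 = 60%. Specificity becomes 0.98 + 0.02 × 0.20 = 98.4%. NPV moves from 94.6% to 95.7%.

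**The case against.** The case against is substantial in four respects.

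- **Timing.** The 1 to 3 days is a general remark about PCR, not a figure for either study laboratory. Visits aim for 24 hours, so many cards may be read before any result exists. No section says when families are told. This stands: a reader might infer that some reads are certainly made with the PCR result in hand, but the documents show only that nothing prevents it.
- **The look-up in section 25.1.** The sentence follows one about referring participants whose at-home test is positive, so it most naturally describes a check after the card is read. It is not evidence of prior knowledge. For Exact Sciences the team must also request the result, and nothing says that this precedes the visit.
- **Traceability.** A reader might infer that affected reads could never be identified. That is too strong: visit times are recorded and could be compared with laboratory release times if those were obtained, and the data collection form is not in the documents. The listed elements, however, include neither release time nor family knowledge.
- **Size.** One can construct a case in which five readings reverse the NPV result. Take 326 PCR-negatives with no false positives and 32 PCR-positives. With 27 misses NPV is 326/353 = 92.4% (p = 0.216); with 22 it is 326/348 = 93.7% (p = 0.044). But 27 misses imply a second-test sensitivity of 5/32 = 16%, against the protocol's expectation that a repeat would nearly always turn positive. With 17 misses NPV is 326/343 = 95.0% and p = 0.003, so the test succeeds without any bias. Nor would the section 20.4 non-inferiority conclusion on sensitivity change: 16% and 31% (10/32) both lie far below 99% − 5% = 94%. The example shows that the NPV test is fragile near its boundary, and no more.

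None of this supplies masking or a record of who knew what.

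**Conclusion.** The point holds as a gap in design and recording. The read is visual, the coordinator takes part in it, its window overlaps the quoted PCR turnaround, and both readers have a possible route to the reference result. Nothing masks the coordinator or records the family's knowledge. Aim 1 sensitivity, specificity and NPV may be overstated. The amount is unknown, because the documents give neither the share of cards read after the result nor the share of readings that would change.

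The only size that can be offered is conditional. At a true NPV of 91%, with 10% of missed positives read toward PCR, false success on the NPV test rises from 4.9% to about 13-14% with the cut-off held at 335, or about 10% with it reset. The required N stays at 358. This is a cheap improvement worth making. It does not show that the results are biased or that the primary conclusion would reverse.

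**What to change.** 1. **Sections 13.3 and 16.5:** request a participant's nasal PCR result, or open the laboratory file containing it, only after that participant's at-home result, including the coordinator's verification, is locked in REDCap. Where ACL returns results without a request, leave the file unopened until then. State in section 25.1 that the look-up follows the lock.
2. **Section 13.4:** record the PCR release time from the laboratory. After the card result is locked, ask whether the family had been told the PCR result before the read. Asking afterwards avoids disclosing the result to the coordinator or prompting the family before the card is read.
3. **Section 20.4:** report NPV, sensitivity and specificity for reads made before the result was known, as a supportive sensitivity analysis. It should not be a gate on the primary conclusion: this subset is also read earlier after the in-school test, so a difference could reflect timing as well as knowledge of PCR.

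Release of the PCR result to school and family is unchanged, so families are not masked; their knowledge is only recorded. The cost is one added question, a release time from the laboratory, a change in the order of the result look-up, and a subset smaller than 358 with wider intervals.

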## PROTOCOL TITLE: SAFE AND HEALTHY SCHOOLS

If the second test is not used during the study, the participant may keep it and use it in the future if they feel confident doing so. If a participant says that they do *not* think that they could accurately do the test on their own, the study coordinator would advise them to seek assistance from a medical provider.

To accomplish the aims of this study, the study team will also need access to the results from the nasal swab antigen and PCR tests collected by the school. Parents will learn the results of the antigen test, and they will share the results with the study coordinator. If the samples are processed at Exact Sciences Laboratories, they will share the test results of the nasal swab and lollipop PCR tests with the study team via Exact Science's instance of HIPAA-secure Box. If the samples are processed by ACL, then the study team will share the results of the nasal swab and lollipop PCR tests with the study team via a UW-Madison Cybersecurity-approved data sharing tool.

- 13.4 A data collection form is uploaded in ARROW. Below is a list of data elements. Note that all data elements will be collected from participants who complete the at-home BinaxNOW test—those whose initial at-school BinaxNOW test was negative. The data elements related to at-home BinaxNOW testing will not be collected from participants whose initial at-school BinaxNOW test was positive, as they will not complete the at-home test virtual visit.
  - Administrative information
    - Dates and locations (i.e., virtual or in-person) of study activities
    - Times of data collection and study activities
    - Confirmation of consent and assent
  - Participant information collected verbally and recorded in REDCap
    - Participant's first and last name
    - Participant's parent or legal guardian (in the case of children)
    - Address
    - Phone Number
    - Email Address
    - Questions about participant's opinions on data collection methods
  - Biosample Collection Date/Time
    - At-school BinaxNOW (collected by school or study team)
    - Nasal swab for PCR testing (collected by school)
    - Lollipop swab
    - BinaxNOW test (administered by participant/family)
  - Biosample Results

## PROTOCOL TITLE: SAFE AND HEALTHY SCHOOLS

- Results of at-school BinaxNOW
- Results of nasal swab PCR collected by school personnel—COVID-19 and, whenever these tests are ordered by the schools, also Influenza A, Influenza B, and cycle threshold (CT) value
- Results of lollipop swab PCR testing—COVID-19, Influenza A, Influenza B, and CT value
- At-home BinaxNOW test result

Source records that will be used to collect data about participants:

- UW Health medical or billing records via ICTR's Clinical Research Data Service (CRDS)
- UW Health HealthLink Records (study team will directly access)
- Data from departmental QA or QI database
- Data from UW Health Enterprise Data Warehouse (EDW)
- Data from PACS (Picture Archiving and Communication System);
- Data from Center for Medicare/Medicaid Services
- Data from publicly available datasets (e.g., U.S. census data)
- Data from outside institutions or organizations (specify:  
\_\_\_\_\_)

Other (specify: Data from Exact Sciences, accessed via Exact Sciences' HIPAA-secure Box, and Data from ACL, exchanged via UW-Madison Cybersecurity-approved data sharing tool )

13.5 The “lollipop” collection swab is a non-significant risk device. It does not meet the definition of “significant risk,” which is a device that presents a potential for serious risk to health, safety or welfare of subjects.

The FDA granted Emergency Use Authorization for the BinaxNOW test.

### 14.0 Comparison of usual care and study procedures

14.1 If individuals want additional testing for COVID-19, they could obtain PCR testing at a variety of locations, such as a local testing center, pharmacy, or their child’s PCP’s office. The parent could also choose to purchase and administer their own BinaxNOW test from a supplier, such as Walgreens or CVS. They may also seek out an alternative type of testing. Cost, convenience, and parent and child willingness are all factors that influence which types of testing may or may not be selected.

14.2 UW Health guidance about COVID-19 testing is described at <https://coronavirus.uwhealth.org/COVID-19-testing/>. Individuals who are

## PROTOCOL TITLE: SAFE AND HEALTHY SCHOOLS

experiencing symptoms of COVID-19 are encouraged to contact their health care providers. The typical guidance for symptomatic patients is to get PCR testing done.

14.3 Standard of care at UW Health for children experiencing one or more [symptoms of COVID-19](#) is a nasal PCR test. Elementary schools are offering nasal PCR tests, so the school's procedures overlap with standard of care at UW Health. The "lollipop" and BinaxNOW testing procedures in this protocol do not overlap with standard clinical care.

14.4 Research participation would not affect standard clinical care.

## 15.0 Withdrawal of Participants

- 15.1 If a participant with a negative at-school BinaxNOW test result does not complete the BinaxNOW at-home test within 5 days (120 hours) of the initial test, they will be withdrawn from the serial antigen testing portion of the study without their consent.
- 15.2 For orderly termination, a study team member will notify the participant that their study participation is complete.
- 15.3 If a participant asked to complete the at-home BinaxNOW test fails to do so, we will still use their lollipop swab results and results of the nasal swabs collected at school to explore Aim 1.

## 16.0 Data Management and Confidentiality

- 16.1 Procedures that will be used for quality control of collected data:

A study team member will watch participants conduct the at-home BinaxNOW test to ensure quality of sample collection and test administration. The result of the test will be verified by the coordinator.

- 16.2 Steps the researchers will take to secure the data:

- Data will be coded, and the "key" linking identities to codes will be kept separately from the data. (applies to lollipop swabs processed by Exact Sciences Laboratories)
- Data will be coded, and the "key" linking identities to codes will be kept on paper only. The study data will be stored electronically and labeled only with codes.
- Only those listed as key personnel will have access to the "key."
- Access to the "key" will be limited to the following person (e.g., Database Administrator): \_\_\_\_\_
- This study is funded by the National Institutes of Health and is covered by a Certificate of Confidentiality.

## PROTOCOL TITLE: SAFE AND HEALTHY SCHOOLS

- This study is NOT funded by the National Institutes of Health but because it will collect sensitive information, the research team will apply for a Certificate of Confidentiality to protect data from being requested without the subject's consent as part of a legal proceeding.
- Other: Data will be stored in REDCap, and all fields containing PHI will be labeled as such. Granting study team member's permission to export data containing PHI will be limited to a need-only basis.

### 16.3 How and where data and/or specimens will be stored and maintained:

- Online Collaborative Research Environment (OnCore) Biospecimen Management
- Research Electronic Data Capture (REDCap) *Specify which instance you will be using (e.g., ICTR's, Department of Medicine's):* ICTR
- Other software option that will be stored on departmental server. *Specify the department:* Pediatrics
- Locked filing cabinet or drawer inside a locked room. *Specify the building:* [name]
- Other (describe): Lollipop specimens will be provided to Exact Sciences Laboratories or ACL for analysis after collection by the end of the day. Lollipop test results will be provided to the study team using Exact Sciences' instance of HIPAA-Secure Box or using a UW-Madison Cybersecurity-approved data sharing tool. ACL, adult participants, or parents of child participants will verbally share the results of the at-school antigen test with the study team.
- Data will not be stored or accessed on portable devices.
- Portable devices will be used to access secure web-based data collection sites such as ICTR's REDCap.
- Data stored on portable devices will be coded with the key stored separately. No identifiers will be stored on portable devices.
- Data stored on portable devices and therefore only encrypted devices will be used.

